**Table 2: Sample Size Justification for the Co-primary Immunogenicity Endpoints**

Primary Endpoint	Number of Evaluable Participants (with 10% ineligible for Per-protocol Set)	$\alpha$	Standard Deviation	GMR/SRR Assumed	NI Margin	Power
mRNA-1345 Noninferiority (2-sided test)						
Day 29 GMT Coadministration (Group 2) vs. alone (Group 1)	378(Group 1) 540(Group 2)	0.05	1.5	GMR=1	1.5	98%
Day 29 SRR Coadministration (Group 2) vs. alone (Group 1)	378 (Group 1) 540 (Group 2)	0.05		SRR=0.8 in both groups	10%	96%
Afluria Quadrivalent Noninferiority (2-sided test) for Each Influenza Strain						
Day 29 GMT Coadministration (Group 2) vs. alone (Group 3)	540 (Group 2) 540 (Group 3)	0.05	1.5	GMR=1	1.5	99%
Overall power to show noninferiority of the primary immunogenicity endpoints						90%

With 540 participants to be included in PP Set in mRNA-1345 + Afluria Quadrivalent (Group 2) and 378 participants to be included in PP Set in mRNA-1345 + placebo (Group 1):

- There is at least 98% power to demonstrate the noninferiority of the immune response to RSV-A, as measured by GMT of RSV-A nAb in participants receiving mRNA-

1345 plus Afluria Quadrivalent compared with that in mRNA-1345 plus placebo group, at a 2-sided alpha of 0.05, assuming a noninferiority margin of 1.5 and an underlying GMR of 1. The standard deviation of the natural log-transformed level is assumed to be 1.5.

- There is at least 96% power to demonstrate the noninferiority of the immune response, as measured by SRR of RSV-A nAbs at Day 29 in participants receiving mRNA-1345 plus Afluria Quadrivalent compared with that in mRNA-1345 plus placebo group, at a 2-sided alpha of 0.05, assuming an SRR of RSV-A nAbs of 80% in both groups (a true SRR difference is 0), and a noninferiority margin of 10%.

With 540 participants to be included in PP Set in either mRNA-1345 plus Afluria Quadrivalent group (Group 2) or Afluria Quadrivalent plus placebo group (Group 3):

- There is at least 99% power to demonstrate noninferiority of the immune response to each of the 4 influenza strains, as measured by GMT of influenza anti-HA Abs for each strain in participants receiving mRNA-1345 plus Afluria Quadrivalent compared with that in Afluria Quadrivalent plus placebo group, at a 2-sided alpha of 0.05, assuming a noninferiority margin of 1.5 and an underlying GMR of 1. The standard deviation of the natural log-transformed level is assumed to be 1.5.

#### **Sample Size and Power for the key secondary immunogenicity endpoints:**

With 540 and 378 participants to be included in PP Set in mRNA-1345 plus Afluria Quadrivalent group (Group 2) and mRNA-1345 + placebo (Group 1), respectively:

- There is at least 98% power to demonstrate the noninferiority of the immune response to RSV-B, as measured by GMT of RSV-B nAb in participants from Group 2 compared with that from Group 1, at a 2-sided alpha of 0.05, assuming a noninferiority margin of 1.5 and an underlying GMR of 1. The standard deviation of the natural log-transformed level is assumed to be 1.5.
- There is at least 96% power to demonstrate the noninferiority of the immune response, as measured by SRR of RSV-B nAbs at Day 29 in participants from Group 2 compared with that from Group 1, at a 2-sided alpha of 0.05, assuming a SRR of 80% in both groups (a true SRR difference is 0) and a noninferiority margin of 10%.

With 540 participants to be included in PP Set in either mRNA-1345 plus Afluria Quadrivalent group (Group 2) or Afluria Quadrivalent plus placebo group (Group 3):

- There is approximately 95% power to demonstrate the noninferiority of the immune response to each of the 4 influenza strains, as measured by SCR of influenza anti-HA

Abs for each strain at Day 29 in participants from Group 2 compared with that from Group 3, at a 2-sided alpha of 0.05, assuming an SCR of 70% in both groups (a true SCR difference is 0) and a noninferiority margin of 10%.

- Under the same assumptions for each strain, the overall power to demonstrate the noninferiority of the immune response to 4 influenza strains is approximately 80%.

#### **2.3.4. Randomization**

The randomization will be in a blinded manner using a centralized IRT, in accordance with pre-generated randomization schedules.

The study will enroll approximately 1620 medically stable adults  $\geq$  50 years of age. Participants will be randomized with a ratio of 7:10:10 to receive either 1) mRNA-1345 + placebo (Group 1, 420 participants); 2) mRNA-1345 + Afluria Quadrivalent (Group 2, 600 participants); or 3) Afluria Quadrivalent + placebo (Group 3, 600 participants). Randomization will be stratified by age (50 to 59 years, 60 to 74 years, and  $\geq$  75 years). The study will target enrollment of approximately 20% of participants 50 to 59 years of age. Randomization details is described in [Section 2.3.1](#).

#### **An IRT error**

On 07-March-2023, the Sponsor was informed of an error in the randomization ratio in Part A. The IRT vendor inadvertently inactivated the enrollment for Group 1 when 959 participants were randomized in Part A as part of a system build to fix an unrelated issue on 25-May-2022. Group 1 remained inactive until 25-Jul-2022 while the enrollment of Part A was completed on 09- June-2022. As a result, approximately 250 participants, instead of protocol planned 420 participants, were randomized in Group 1. This IRT error caused an under enrollment of around 170 participants in Group 1 and an over enrollment in Group 2 and 3; and the actual ratio for participants randomized in the three Groups was approximately 5:14:14.

The above information was received after the EDC database of Part A was locked but before the selected Sponsor and CRO personal, as defined by the study Data Blinding Plan, are to be unblinded to perform the analyses, and before the immunogenicity data become available. The assessment of actual randomization ratio was also conducted in a blinded fashion.

#### **2.3.5. Blinding and Unblinding**

This is an observer-blind study. The investigator, study staff, study participants, site monitors, and Sponsor personnel (or its designees) will be blinded to the IP administered until the study database is locked and unblinded, with certain exceptions, please refer to Section 2.5.2 of the protocol and Data Blinding Plan for details.

Planned analyses are described in [Section 2.5.6](#) of the SAP and Section 2.8.6 in the protocol. At the primary analysis, pre-identified Sponsor team members and selected CRO team members as specified in the study Data Blinding Plan will be unblinded to conduct the analyses. Meanwhile, a separated blinded biostatistics and programming team will be in place until the database lock for the Final Analysis. Participants and investigators will remain blinded until the end of this study.

Except in the case of medical necessity, a participant's vaccine assignment should not be unblinded without the approval of the Sponsor. If a participant becomes seriously ill or pregnant during the study, the blind will be broken only if knowledge of the vaccine assignment will affect that participant's clinical management. In the event of a medical emergency requiring identification of individual vaccine assignment, the investigator will make every attempt to contact the Sponsor medical lead or designee, preferably via electronic protocol inquiry platform, to explain the need for unblinding within 24 hours of obtaining the treatment code. The investigator will be responsible for documenting the time, date, reason for unblinding, and the names of the personnel involved. The investigator (or designee) will have access to unblind participants within IRT. All unblinding instances will be tracked via an audit trail in IRT and documented in the final CSR.

## **2.4. Analysis Populations**

Analysis populations for statistical analyses are Randomization Set, Full Analysis Set, PP Set, Supportive PP Set, Solicited Safety Set, and Safety Set.

### **2.4.1. Randomization Set**

The Randomization Set consists of all participants who are randomized in the study, regardless of the participant's treatment status in the study. Participants will be included in the vaccination group to which they are randomized.

### **2.4.2. Full Analysis Set**

The FAS consists of all randomized participants who receive any study injection. Participants will be analyzed according to the vaccination group to which they are randomized.

### **2.4.3. Per-protocol Set**

#### **PP Set**

The PP Set consists of all participants in the FAS who receive the assigned study injections according to protocol, comply with immunogenicity blood sampling to have a baseline and at least one Day 29 post-injection assessment within the visit window of study day [22, 43], and have no major protocol deviations that impact the immune response.

The PP Set will be the primary population used for the analysis of immunogenicity data, and Participants will be included in the vaccination group to which they are randomly assigned.

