### **2.5.4. Study Intervention Compliance**

The IP will be administered at the study site under direct observation of medically qualified unblinded study personnel and appropriately recorded (date and time) in the source documents and eCRF. The qualified unblinded study personnel will confirm that the participant has received the entire dose of the IP, record the injection site (left or right deltoid) and corresponding IP administered, and keep the information confidential from other study documents and study personnel until unblinding is authorized. If a participant does not receive the IP or does not receive all of the planned dose, the reason for the missed dose will be recorded. The data will be reconciled with the study site accountability records to assess compliance.

The study site staff are responsible for ensuring that the participants comply with the allowed study visit windows. If a participant misses a visit, every effort should be made to contact the participant and complete the visit within the defined visit window, as specified in the SoA ([Table 1](#) [Part A] or [Table 7](#) [Part B]). If a participant does not complete a visit within the defined time window, that visit will be classified as a missed visit, and the participant will continue with the subsequent scheduled visits. All safety requirements of the missed visit will be captured and included in the subsequent visit.

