#### **2.5.5.3. Concomitant Medications and Vaccines That May Lead to the Elimination of a Participant from the Per-Protocol Analyses**

The use of the following concomitant medications and/or vaccines will not require withdrawal of the participant from the study but may determine a participant's evaluability in the per-protocol (PP) analysis (analysis sets are described in [Section 2.8.4](#)):

- Any investigational or nonregistered product (drug or vaccine) other than the IPs used during the study period.
- A nonstudy vaccine (including authorized or approved vaccines for the prevention of COVID-19 regardless of the type of vaccine) administered during the period from 28 days before through 28 days after the study injection.
- Immunoglobulins and/or any blood products administered during the study period (except for treatment of COVID-19).

- Medications that suppress the immune system (except for treatment of COVID-19).

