### 3.4. Analysis Populations

Please see [Section 2.4](#) for details, except of the following:

- Supportive PP Set will not be applicable in Part B.
- PP Set consists of all participants in the FAS who receive the assigned Day 1 study injections according to protocol regardless of Day 29 injection, comply with immunogenicity blood sampling to have a baseline and at least one Day 29 post-injection assessment within the visit window of study day [22, 43], and have no major protocol deviations that impact the immune response.
- Additionally, 2 subsets of the Solicited Safety Set are defined for Day 1 injection and Day 29 injection. Day 1 (Day 29) Solicited Safety Set consists of all participants in the Solicited Safety Set who have received the study injection on Day 1 (Day 29) and have contributed any solicited AR data (eDiary) from the time of study injection on Day 1 (Day 29) through the following 6 days.

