## 7.9. Appendix I      Estimands and Estimand Specifications

**Table 8:      Intercurrent Events**

Label	Intercurrent Event Type
IcEv1 (early discontinuation or unrelated death)	Early discontinuation from study or unrelated death prior to Day 29, the first post-treatment immunogenicity result available.
IcEv2 (Alternative RSV vaccine, flu vaccine or SARS-CoV-2 vaccine)	Use of alternative RSV vaccine, flu vaccine or SARS-CoV-2 vaccine prior to Day 29.
IcEv3 (Prohibited medications)	Use of prohibited medications deemed to impact on immunogenicity prior to Day 29.

Abbreviation: IcEv: intercurrent event; RSV: respiratory syncytial virus.

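### The SAP lets the Day 29 co-primary sample run to Day 43, but the nonstudy-vaccine exclusion, two intercurrent-event cut-offs and the Part B pre-injection condition were not carried with it

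*SAP*

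**What the plan says.** **Window.** SAP 2.4.3 (Part A) and 3.4 (Part B) admit a participant to the PP Set with "at least one Day 29 post-injection assessment within the visit window of study day [22, 43", and Appendix B Tables 5 and 6 use the same limits. Protocol Tables 1 and 7, reprinted in SAP Appendices F and G, give the Day 29 visit a window of 7 days before to 2 days after. Protocol 2.5.4, which Part B adopts through 3.5.4, says: "If a participant does not complete a visit within the defined time window, that visit will be classified as a missed visit". The participant then continues with the next scheduled visit.

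**Exposure rules.** Protocol 2.5.5.3 lists four exposures that may remove a participant from the PP analysis. One is a nonstudy vaccine "administered during the period from 28 days before through 28 days after the study injection". Two others have a different reach: "Any investigational or nonregistered product (drug or vaccine) other than the IPs used during the study period" and "Immunoglobulins and/or any blood products administered during the study period (except for treatment of COVID-19". The fourth, immunosuppressive medication, has no end date. In SAP Table 8, IcEv3 is "Use of prohibited medications deemed to impact on immunogenicity prior to Day 29", and IcEv2 (alternative RSV, influenza or SARS-CoV-2 vaccine) has the same cut-off.

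**Part B order.** Footnote e of protocol Table 7 and of SAP Appendix G requires blood before study product on vaccination days. The Part B PP Set takes participants "who receive the assigned Day 1 study injections according to protocol regardless of Day 29 injection". Appendix B maps scheduled samples to their nominal visit, and unscheduled or early-termination samples by study day alone.

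**The concern.** All six co-primary immunogenicity endpoints in each of Parts A and B rest on this one sample, and all six must succeed. The two documents give a draw on Days 32 to 43 different status: a missed visit in the protocol, a valid per-protocol result in the SAP. The primary estimands describe a population free of intercurrent events, yet for a late sample the stated rules do not cover the whole interval up to the draw. A licensed vaccine given in that interval would break no dated rule. If it contained an antigen under test and was given in both arms, it would tend to raise both sets of titers and narrow the difference between them, which favours noninferiority. In Part B, a Group 4 sample taken after that group's Day 29 mRNA-1273.214 injection would no longer represent mRNA-1345 given alone.

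**Working it through.** The plan states no figure for this point, so the check is date arithmetic plus a comparison of the passages.

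1. **Protocol window** (Tables 1 and 7): 29 − 7 = Day 22 and 29 + 2 = Day 31. Width 31 − 22 + 1 = 10 days.
2. **SAP window** (2.4.3, 3.4, Tables 5 and 6): Days 22 to 43. Width 43 − 22 + 1 = 22 days. The extra days are 32 to 43, so 43 − 31 = 12.
3. **Other windows.** Day 181 is [167, 195] and Day 211 is [197, 225]; both equal the protocol's ±14. Part B Day 57 is [50, 71], which is 57 − 7 to 57 + 14, against ±5 in the protocol. Day 29 has the same shape: 29 − 7 = 22 and 29 + 14 = 43. The width therefore looks like a chosen convention rather than a slip, but SAP Section 5 does not mention it.
4. **Nonstudy-vaccine rule.** Twenty-eight days after a Day 1 injection is 1 + 28 = Day 29, the last covered day. Before a Day 43 sample, Days 30 to 42 are uncovered: 42 − 30 + 1 = 13 days.
5. **IcEv2 and IcEv3.** The last covered day is Day 28. Before a Day 43 sample, Days 29 to 42 are uncovered: 42 − 29 + 1 = 14 days.
6. **Same gaps at the protocol limit.** Before a Day 31 sample, Day 30 (1 day) and Days 29 to 30 (2 days) are uncovered. The gap comes almost entirely from the wider window, but narrowing the window alone would not quite close it.
7. **Rules with no gap.** Two rules run for the study period and one has no end date. In Part B, if the nonstudy-vaccine rule also runs from the second injection, it extends to 29 + 28 = Day 57 and has no gap.
8. **Part B comparisons exposed.** On Day 29, Group 4 receives mRNA-1273.214 and Groups 5 and 6 receive placebo. A misplaced post-injection sample therefore matters for RSV-A (co-primary) and RSV-B (key secondary) in Group 5 versus Group 4. It does not matter for the SARS-CoV-2 endpoints in Group 5 versus Group 6.
9. **Size.** The documents give no count of late samples. For scale only, assume 2% to 5% of a Part B group of 560: 0.02 × 560 ≈ 11 and 0.05 × 560 = 28 late samples. Only those with an exposure in the gap would be affected.

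**The case against.** An analysis window may be wider than a visit window. The protocol's PP Set needs only one post-injection assessment and states no Day 29 window, so on timing the SAP is the stricter document, and it says that it prevails where methods differ. This stands: the width alone is not a fault.

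A reader might infer that all the disqualifying-exposure rules stop at Day 29. They do not; three of the four rules in protocol 2.5.5.3 carry no such limit. The gap is confined to the nonstudy-vaccine rule, read from the Day 1 injection, and to IcEv2 and IcEv3.

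A reader might also infer that Part B lets the sample follow the Day 29 injection. Footnote e in both documents says otherwise. Blood and injection belong to the same visit, and no blood is scheduled at Day 37 or at unscheduled visits. Scheduled samples keep their nominal visit, and where several samples fall in one window the closest to target is used. What remains is an unscheduled post-injection draw by Day 43 that nothing in the PP definition or mapping would reject.

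Table 8 describes Day 29 under IcEv1 as the first available post-treatment result, so IcEv2 and IcEv3 could be read as ending at the Day 29 assessment. The Sponsor can also exclude major deviations before lock and unblinding (SAP 2.5.2.7). Both readings are possible, but the documents adopt neither for a Day 32 to 43 draw.

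**Conclusion.** The point holds in limited form. The documents disagree on whether a sample on Days 32 to 43 is missed or per-protocol, and the change is not declared. Taken literally, the nonstudy-vaccine exclusion leaves up to 13 days, and IcEv2 and IcEv3 up to 14 days, uncovered before a Day 43 sample. The 13-day figure assumes the vaccine rule runs from the Day 1 injection; the 14-day figure assumes Day 29 means the study day. Part B has a separate, smaller gap: the required order of blood before injection is not enforced in the analysis rules, and only the RSV comparisons of Group 5 with Group 4 could be affected.

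The documents do not support a claim that the co-primary results are materially biased. The effect is probably small and cannot be computed without the number of late samples and the exposures before them.

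**What to change.** 1. Define the nonstudy-vaccine PP exclusion and IcEv2/IcEv3 as exposure before the date of the Day 29 sample actually used. This also settles which injection the vaccine rule runs from in Part B.
2. In the Part B PP definition and in Appendix B, count as Day 29 only a sample taken before the Day 29 injection. Participants without that injection satisfy the condition automatically.
3. Reconcile the [22, 43] window with protocol 2.5.4 and Tables 1 and 7, or state and justify it in SAP Section 5. In either case, say whether a draw on Days 32 to 43 is a major deviation.

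This is mostly SAP wording, with no added visits or participants. The cost is that a few late-sampled participants with an interim exposure leave the PP Set. For Part A the change affects the analysis rules only. SAP 2.3.4 reports enrolment complete on 9 June 2022 and the EDC database already locked by March 2023, so no schedule amendment can alter Part A sampling.

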### **Supportive PP Set**

The Supportive PP Set consists of all Group 1 and Group 2 participants in the PP Set from mRNA-1345-P302 and participants from mRNA-1345-P301 who are in the Per-protocol Immunogenicity Set, received one injection of mRNA-1345 (█ CC1 µg) during April to June of 2022, and were in the Phase 3 segment from U.S sites. Please refer to Section 5.5 of mRNA-1345-P301 SAP for detailed definition of the Per-protocol Immunogenicity Set. The Supportive PP Set will be the analysis set for a supportive analysis of the primary immunogenicity endpoints of RSV-A nAbs and the key secondary immunogenicity endpoints of RSV-B nAbs to mitigate the IRT error as indicated in [Section 2.3.4](#). The participants from mRNA-1345-P301 and the Group 1 participants from mRNA-1345-P302 will be pooled together and compared with the Group 2 participants from mRNA-1345-P302.

### **2.4.4. Safety Set**

The Safety Set consists of all randomized participants who receive any study injection. The Safety Set will be used for all analyses of safety except for the solicited ARs.

Participants will be included in the vaccination group corresponding to the study injections that they actually received.

### **2.4.5. Solicited Safety Set**

The Solicited Safety Set consists of all participants in the Safety Set who contribute any solicited ARs data, i.e., have at least one post-baseline solicited safety assessment.

The Solicited Safety Set will be used for the analyses of solicited ARs and participants will be included in the vaccination group corresponding to the study injections that they actually received.

## **2.5. Statistical Analysis**

### **2.5.1. General Considerations**

The Schedule of Assessments is provided in [Appendix F](#).

**Continuous variables** will be summarized using the following descriptive summary statistics: the number of participants (n), mean, standard deviation (SD), median, minimum (min), and maximum (max). For the summary statistics of all numerical variables, unless otherwise specified, the display precision will follow programming standards. Please see [Appendix A](#) for variable display standards.

**Categorical variables** will be summarized using counts and percentages. When count data are presented, the percentage will be suppressed when the count is zero to draw attention to the non-zero counts. A row denoted “Missing” will be included in count tabulations where specified on the shells to account for dropouts and missing values. The denominator for all percentages will be the number of participants in that vaccination group within the analysis set of interest, unless otherwise specified.

**Baseline value** is defined as the most recent non-missing measurement (scheduled or unscheduled) collected before the first injection, unless otherwise specified. For immunogenicity tests, the baseline is defined as the most recent non-missing result/measurement (scheduled or unscheduled) collected before or on the date of the first injection (Day 1). If there are multiple valid results on the same date, the largest value will be considered in the immunogenicity baseline derivation.

**Study day relative to the Day 1 injection** will be calculated as below:

- a) Study day prior to the Day 1 injection will be calculated as: date of assessment/event – date of the Day 1 injection (resulting in negative study day).
- b) Study day on or after the date of the Day 1 injection will be calculated as: date of assessment/event – date of the Day 1 injection + 1.

For GMT and GMC calculation, antibody values reported as below the LLOQ will be replaced by  $0.5 \times \text{LLOQ}$  and antibody values greater than the ULOQ will be converted to the ULOQ.

**Unscheduled visits:** Unscheduled visit measurements will be included in analysis as follows:

- In the derivation of baseline measurements.
- In scheduled visit windows per specified visit windowing rules.
- In individual participant data listings as appropriate.

**Visit windowing rules:** The analysis visit windows for protocol-defined visits are provided in [Appendix B](#), Table 5.

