**Incomplete/missing data:**

- Imputation rules for missing dates of prior/concomitant medications and non-study vaccinations are provided in [Appendix C](#).
- Imputation rules for missing dates of prior/concomitant procedures are provided in [Appendix D](#).
- Imputation rules for missing AE dates are provided in [Appendix E](#).

- Other incomplete/missing data will not be imputed, unless specified otherwise.

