#### **2.5.4.2.2. Sensitivity Analysis**

Analyses of the primary endpoints will be performed based on the FAS, using the same method and same definition as described in [Section 2.5.4.2.1](#).

This sensitivity analysis corresponds to the Supportive Immune Estimands 1b-3b as described in [Appendix I](#), Table 9.

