#### **2.5.4.4. Analysis of Other Secondary Immunogenicity Endpoints**

The secondary immunogenicity endpoints include the following:

- GMT and GMFR of post-injection/baseline titers to RSV-A nAbs up to Day 181/EoS
- GMT and GMFR of post-injection/baseline titers to RSV-B nAbs up to Day 181/EoS
- SRR and proportion of participants with  $\geq$  2-fold increases in RSV-A nAb titers up to Day 181/EoS
- SRR and proportion of participants with  $\geq$  2-fold increases in RSV-B nAb titers up to Day 181/EoS.
- SCR and proportion of participants with  $\geq$  2-fold increases in influenza anti-HA Abs for each influenza strain at Day 181/EoS
- GMT and GMFR of influenza anti-HA Abs for each influenza strain up to Day 181/EoS

The statistical analyses are:

- GMT of RSV-A nAbs, RSV-B nAbs, and influenza anti-HA Abs for each influenza strain with corresponding 95% CI will be provided at Baseline (Day 1), Day 29, and Day 181/EoS by vaccination group. The 95% CIs will be calculated based on the t-distribution of the log-transformed values and then back transformed to the original scale for presentation. The following descriptive statistics will also be provided at Baseline (Day 1), Day 29, and Day 181/EoS: the number of participants (n), median, minimum and maximum. GMT with 95% CI will be plotted at Baseline (Day 1) and Day 29 by vaccination group.
- GMFR of RSV-A nAbs, RSV-B nAbs, and influenza anti-HA Abs for each influenza strain with corresponding 95% CI will be provided at Day 29 and Day 181/EoS over pre-injection at Day 1 [baseline] by vaccination group. The 95% CIs will be calculated based on the t-distribution of the difference in the log-transformed values (post-baseline time point – Day 1) and then back transformed to the original scale for presentation. GMFR with 95% CI will be plotted at Day 29 by vaccination group.

- Proportion of participants with  $\geq$  2-fold increases from Day 1 (baseline) in RSV-A nAb titers, RSV-B nAb titers, and influenza anti-HA Abs for each influenza strain at Day 29 and Day 181/EoS will be provided with 2-sided 95% CIs using the Clopper-Pearson method by vaccination group.
- SRR in RSV-A nAb titers and RSV-B nAb titers and SCR in influenza anti-HA Abs for each influenza strain at Day 181/EoS will be provided with 2-sided 95% CIs using the Clopper-Pearson method by vaccination group.

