- SRR in RSV-A nAb titers, RSV-B nAb titers, and SARS-CoV-2 nAbs for each SARS-CoV-2 strain (Wuhan-Hu-1 and B.1.1.529) at Day 29, Day 57, Day 181, and Day 211/EoS will be provided with 2-sided 95% CIs using the Clopper-Pearson method by vaccination group.

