- Proportion of participants with  $\geq 2$ -fold increase from primary dose Day 1 (baseline) in RSV-A nAb titers and RSV-B nAb titers at primary dose Day 29, primary dose Day 181, BD Day 1, BD Day 29, BD Day 181, and BD Day 361/EoS will be provided with 2-sided 95% CIs using the Clopper-Pearson method by vaccination group.
- SRR in RSV-A nAb titers and RSV-B nAb titers at primary dose Day 29, primary dose Day 181, BD Day 1, BD Day 29, BD Day 181, and BD Day 361/EoS will be provided with 2-sided 95% CIs using the Clopper-Pearson method by vaccination group.

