IcEv1 (early discontinuation or unrelated death)	Principal stratum		
IcEv2 (Alternative flu vaccine)	Principal stratum		
IcEv3 (Prohibited medications)	Principal stratum		
Rationale for Strategies	Besides the rationale for strategies as indicated in Estimand 1a, this estimand also seeks to mitigate the statistical power reduction due to the IRT error occurred.		
Objective: To evaluate the impact of coadministered influenza vaccine on the immune response to RSV based on seroresponse from baseline			
Estimand Label	Primary Immune Estimand 2a (on the PP Set)	Supportive Immune Estimand 2b (on the FAS Set)	

Estimand Description	Immune response to RSV measured as SRR difference of RSV-A neutralizing Ab at Day 29 in adults $\geq$ 50 years old who receive IP administration and complied with immunogenicity blood sampling to have a baseline and at least 1 Day 29 assessment without major protocol deviations impacting immune response.	Immune response to RSV measured as SRR difference of RSV-A neutralizing Ab at Day 29 in adults $\geq$ 50 years old who receive IP administration irrespective of any major protocol deviations impacting immune response and complied with immunogenicity blood sampling to have a baseline and at least 1 Day 29 RSV-A neutralizing Ab assessment.
Target Population	Adults aged 50 years or older who receive the assigned IP administration, complied with immunogenicity blood sampling to have a baseline and at least 1 Day 29 RSV-A neutralizing Ab assessment after the IP administration, and have no major protocol deviations impacting the immune response.	Adults aged 50 years or older who receive any IP administration and complied with immunogenicity blood sampling to have a baseline and at least 1 Day 29 RSV-A neutralizing Ab assessment.
Endpoint	SRR of RSV-A neutralizing Abs at Day 29 (see Section 2.5.4.2.1).	As per Estimand 2a.
Treatment Conditions	mRNA-1345 + Afluria Quadrivalent (Test) vs. mRNA-1345 plus placebo (Reference)	As per Estimand 2a.
Population-Level Summary	Immune response to RSV defined as SRR difference of RSV-A neutralizing Ab using Miettinen-Nurminen's method.	As per Estimand 2a.
Intercurrent Event Strategy		
IcEv1 (early discontinuation or unrelated death)	Principal stratum	Principal stratum
IcEv2 (Alternative flu vaccine)	Principal stratum	Treatment policy

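### As SAP 2.5.1 is written, seroresponse, seroconversion and fold-rise rates after Day 29 are divided by the whole per-protocol set, so missing samples lower them

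*SAP*

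**What the plan says.** SAP 2.5.1 (General Considerations) sets the base for percentages: "The denominator for all percentages will be the number of participants in that vaccination group within the analysis set of interest, unless otherwise specified". The same section deals with missing dates and then adds: "Other incomplete/missing data will not be imputed, unless specified otherwise". Sections 3.5.1 and 4.5.1 adopt 2.5.1 for Parts B and C and list only differences. None of these concerns denominators.

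The later-visit rates are planned as follows:

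- Part A, SAP 2.5.4.4: "SRR in RSV-A nAb titers and RSV-B nAb titers and SCR in influenza anti-HA Abs for each influenza strain at Day 181/EoS", with Clopper-Pearson intervals by group. The 2-fold proportions are reported at Day 29 and Day 181.
- Part B, SAP 3.5.4.4: SRR and 2-fold proportions "at Day 29, Day 57, Day 181, and Day 211/EoS will be provided with 2-sided 95% CIs using the Clopper-Pearson method by vaccination group".
- Part C, SAP 4.5.4.3: the same rates at primary-dose Days 29 and 181 and at "BD Day 1, BD Day 29, BD Day 181, and BD Day 361/EoS will be provided with 2-sided 95% CIs".

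The PP Sets in SAP 2.4.3 and 3.4 require a baseline sample and a Day 29 sample in the window. The Part C PP Set in 4.4.2 requires a pre-booster sample and a BD Day 29 sample. None requires a later sample. Protocol 2.8.5.1, 3.8.1.1 and 4.8.5.1 also plan seroresponse rates at each post-baseline visit without naming a denominator.

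**The concern.** The general rule keeps everyone in the set in the denominator at every visit. A person with no titer cannot meet a titer-based definition of response, so that person lowers the rate exactly as a true non-responder would. The later rates are meant to describe persistence of the immune response. Under this rule they would mix waning with missed visits and dropout.

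The geometric mean titer (GMT) and geometric mean fold rise (GMFR) in SAP 2.5.4 are averages over observed titers. The GMT row and the SRR row for one visit would then describe different participants, and a reader could not tell how much of a fall in SRR is biological.

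**Working it through.** **The plan's own figures first.** The stated SRR power is 96% in Part A (378 vs 540) and 97.8% in Part B (504 per group), with SRR 80% in both groups and a 10-point margin. By the normal approximation, power = Φ(0.10/√[0.8 × 0.2 × (1/n₁ + 1/n₂)] − 1.96).

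- Part A: 0.10/√[0.16 × (1/378 + 1/540)] = 0.10/0.02683 = 3.728. Subtracting 1.96 gives 1.768, so power is 96.15%.
- Part B: 0.10/√[0.16 × 2/504] = 0.10/0.02520 = 3.969. Subtracting 1.96 gives 2.009, so power is 97.77%.

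Both reproduce. Neither depends on the denominator rule, because a Day 29 sample is a condition of entry to the PP Set.

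**Later visits.** Let N be the number in the group within the PP Set, m the share without a result at the visit, and p the true response rate. Missingness is taken as unrelated to response. Responders counted = N(1 − m)p. Dividing by N gives a reported rate of p(1 − m). Dividing by the number observed, N(1 − m), gives p.

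The documents give no missing-sample rate for any visit. The only related planning figure is about 10% ineligible for the PP Set for all reasons. The range 2–15% is therefore an assumption.

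| True rate | m = 2% | m = 5% | m = 10% | m = 15% |
|---|---|---|---|---|
| 80% | 78.4% | 76% | 72% | 68% |
| 60% | 58.8% | 57% | 54% | 51% |
| 40% | 39.2% | 38% | 36% | 34% |

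**Scale against the interval.** Take N = 504, the planned Part B PP size per group, with p = 80% and m = 10%. By the normal approximation the literal rule gives 72% ± 1.96√(0.72 × 0.28/504) = 72% ± 3.9 points, about 68.1% to 75.9%. That interval excludes the true 80%. The observed-sample rule gives 80% ± 1.96√(0.16/453.6) = 80% ± 3.7 points.

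**Across visits and groups.** Day 29 has full denominators, so a constant true 80% with 10% missing later would read as a fall from 80% to 72% with no waning at all. If missingness differs between groups, for example 10% against 5%, equal true rates of 80% would read as 72% and 76%.

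**The case against.** The strongest reply is that no passage says a participant without a sample is a non-responder. Seroresponse is defined on an actual titer, and the no-imputation sentence in 2.5.1 could be read as excluding such participants. Section 2.5.1 also allows a row for missing values where the table shells call for one. The shells are not among the documents and may set a per-visit n. The GMT tables show n at each visit, so missing samples would be visible there.

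Part of this stands: the shells could resolve the point, and the non-responder scoring follows from applying the rule rather than from a stated intention. But leaving a titer blank while keeping the person in the base is not imputation in the SAP's sense, and it still lowers the rate. The SAP names a percentage base where it wants a particular one, as in 2.5.2.1 and 2.5.3.2. It does not do so for these proportions.

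It is also fair that these are descriptive secondary endpoints. Sections 2.5.5 and 3.5.5 say that the other secondary immune endpoints are not controlled for multiplicity. The Part C paired SRR difference at BD Day 29 is model-based in the same participants and is not a count over set size.

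**Conclusion.** Wrong as written, for descriptive secondary endpoints. Applied literally, the rule lowers each SRR, SCR and fold-rise rate after Day 29 by the factor (1 − m): 4 points at a true 80% with 5% missing, and 8 points with 10%. The size rests on an assumed m and on missingness unrelated to response. The conclusion also assumes that the unseen shells do not override the rule.

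Two stronger readings are tempting, and the documents do not support them.

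- A reader might infer that the supportive non-inferiority check of SRR in the full analysis set (FAS) is biased, because "The FAS consists of all randomized participants who receive any study injection" with no sample required, and 2.5.4.2.2 says "Analyses of the primary endpoints will be performed based on the FAS, using the same method and same definition as described in" the primary approach. However, SAP 2.5.4 and 3.5.4 tie the FAS analyses to Appendix I. Estimand 2b there covers participants who "complied with immunogenicity blood sampling to have a baseline and at least 1 Day 29 RSV-A neutralizing Ab assessment", and 6b and 8b set matching conditions. Discontinuation before Day 29 is handled by principal stratum. For Day 29, then, the SAP does specify otherwise.
- A reader might infer that the co-primary PP test scores a missing assay as non-response, because the PP definition does not name the assay. Estimands 2a, 6a and 8a require a Day 29 result for the analyte concerned.

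The co-primary and key secondary Day 29 tests on the PP Set are essentially unaffected.

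**What to change.** Add to SAP 2.5.1, carried by reference to 3.5.1 and 4.5.1: for SRR, SCR and the 2-fold and 4-fold proportions, the denominator at each visit is the number of participants in the analysis set with a non-missing baseline and a non-missing result for that assay at that visit. Show that n beside each rate.

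Optionally, repeat the Appendix I population in 2.5.4.2.2 and 3.5.4.2.2. The latter should also point to 3.5.4.2.1, because it now points to 3.5.4.1, which only lists the assays.

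The cost is SAP wording and table shells. No design, data or hypothesis changes. Intervals at late visits rest on fewer participants. With N = 504, m = 10% and p = 80%, the half-width is 3.7 points, against 1.96√(0.16/504) = 3.5 had every sample been present. Observed-sample rates do not cure dropout that is related to response, but the displayed n lets the reader judge it.
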